3 STUDY OBJECTIVES AND DESIGN

3.1 Study Objectives

3.1.1 Primary Objectives

The primary objectives are to:

- Determine the clinical benefit of ASP2215 therapy in subjects with FMS-like tyrosine kinase (FLT3) mutated AML who are refractory to or have relapsed after first-line AML therapy as shown with overall survival (OS) compared to salvage chemotherapy.
- Determine the efficacy of ASP2215 therapy as assessed by the rate of complete remission and complete remission with partial hematological recovery (CR/CRh) in subjects with FLT3 mutated AML who are refractory to or have relapsed after first-line AML therapy.

3.1.2 Secondary Objectives

The key secondary objectives are to:

- Determine the overall efficacy in event-free survival (EFS) of ASP2215 compared to salvage chemotherapy.
- Determine the overall efficacy in complete remission (CR) rate of ASP2215 compared to salvage chemotherapy.

The secondary objectives are to evaluate the safety and efficacy of ASP2215 therapy versus salvage chemotherapy in terms of:

- Leukemia-free survival (LFS)
- Duration of remission
- Complete remission with partial hematologic recovery (CRh) rate
- Composite complete remission (CRc=CR+CRp+CRi) rate
- Transfusion conversion rate; Transfusion maintenance rate
- Transplantation rate
- Patient reported fatigue (Brief Fatigue Inventory [BFI])
- Adverse events (AEs), safety labs, vital signs, ophthalmologic exams, electrocardiograms (ECGs) and Eastern Cooperative Oncology Group (ECOG) performance scores
- Evaluation of ASP2215 (and metabolites as appropriate) plasma concentration and population pharmacokinetics (PK)

3.1.3 Exploratory Objectives:

Evaluate the safety and efficacy of ASP2215 therapy versus salvage chemotherapy in terms of:

- Pharmacogenomics (PGx)
- FLT3 gene mutation status
 - o mutation types and frequency
 - o relationship to efficacy and safety
 - mechanisms of acquired resistance
- Exploratory (predictive) biomarkers of ASP2215 activity
- Resource utilization in this study population including hospitalization, blood transfusion, antibiotic intravenous infusions, medication for AEs and opioid usage
- Patient reported dyspnea (Functional Assessment of Chronic Illness Therapy-Dyspnea-Short Forms [FACIT-Dys-SF])
- Patient reported signs, symptoms and impacts of AML (Functional Assessment of Cancer Therapy-Leukemia [FACT-Leu], dizziness and mouth sore items)
- EuroQol Group-5 Dimention-5 Level Instrument (EQ-5D-5L)

3.2 Study Design

3.2.1 Study Design

This is a phase 3, open-label, multicenter, randomized study to compare the efficacy and safety of ASP2215 therapy to salvage chemotherapy in FLT3-mutated AML subjects who are refractory to or have relapsed after first-line AML therapy. Approximately 140 centers in North America, Europe, Asia and rest of the world will participate in this study.

Three hundred sixty nine subjects will be randomized. The randomization of the 369 subjects will be in a 2:1 ratio to receive ASP2215 or salvage chemotherapy. Subjects will enter the screening period up to 14 days prior to the start of treatment. Prior to randomization, the Investigator will preselect a salvage chemotherapy regimen for each subject; options will include LoDAC, azacitidine, MEC or FLAG-IDA. The randomization will be stratified by response to first-line therapy and preselected salvage chemotherapy. Subjects will be administered treatment over continuous 28-day cycles and per institutional guidelines for chemotherapy product preparation and administration. The dose and duration of study treatments are outlined in Section 5.1.1 of the protocol.

For subjects taking ASP2215, LoDAC or azacitidine, treatment should continue until the subject meets a treatment discontinuation criterion.

Subjects receiving MEC or FLAG-IDA will receive 1 cycle of therapy and will be assessed for response on or after day 15, per institutional guidelines. If the bone marrow cellularity is

20% or greater with at least a 50% reduction in blasts, the subject may receive a second cycle of the same chemotherapy. If bone marrow cellularity is between 5% and 20%, the investigator should make the decision whether the subject should receive another treatment cycle or be observed for recovery. If bone marrow cellularity is 5% or less, the subject will be observed for recovery. Subjects achieving CR, CRi or CRp may receive a second cycle of chemotherapy at the Investigator's discretion. Subjects with no response (NR) or progressive disease following cycle 1 will discontinue study treatment.

Dose adjustments for ASP2215 are described in Section 5.1.2 of the protocol.

Subjects who have a donor identified and achieve a response allowing them to undergo HSCT per each institution's assessment can undergo HSCT without leaving the study. However, ASP2215 should be stopped and a pre-HSCT visit should be performed prior to starting the conditioning regimen for HSCT. ASP2215 can be resumed after stem cell transplantation if the following conditions are met:

- Subject is between 30 60 days post HSCT
- Subject has had successful engraftment as demonstrated by absolute neutrophil count $(ANC) \ge 500/mm3$ and platelets $\ge 20000/mm3$ without transfusions
- Subject does not have \geq grade 2 acute graft-versus-host-disease (GVHD)
- Subject is in CRc

For subjects resuming treatment, subjects will follow the procedures listed under subsequent cycles day 1 in the Schedule of Assessments. Subjects who do not resume ASP2215 will be followed for OS endpoint.

After treatment discontinuation, subjects will have a pre-HSCT/end of treatment visit within 7 days after treatment discontinuation, followed by a 30-day follow-up visit in which a telephone contact with the subject is sufficient unless any assessment must be repeated for resolution of treatment-related AEs. After which the subjects will enter the long-term follow-up period for collection of patient reported outcome (PRO) using EQ-5D-5L, subsequent AML treatment, remission status and survival (cause of death and date of death). The long-term follow-up will be every 3 months, for up to 3 years from the subject's end of treatment visit.

Two interim analyses by an Independent Data Monitoring Committee (IDMC) will be conducted. The first interim analysis is planned when approximately 141 subjects are randomized into ASP2215 arm and at least 112 days (4 treatment cycles) post first dose or randomization (for subjects who received no study drug). The first interim analysis will be performed to evaluate the efficacy endpoint of CR/CRh rate and the study conduct will not be impacted by the result of the CR/CRh rate.

The second interim analysis will be performed when approximately 50% of the planned total number of deaths (death events =129 of planned 258 death events) by any cause have occurred. The second interim analysis will be utilized to determine whether the study should be terminated earlier than planned if ASP2215 has more favorable or harmful outcome than

the salvage chemotherapy group. Details of the interim analyses are described in Section 7.10.

The End of Study analysis will be performed on safety data only.

3.3 Randomization

Randomization and study drug assignment will be performed via Interactive Response Technology (IRT). Prior to the initiation of the study treatment, the site staff will contact the IRT in order to determine the randomly assigned treatment. Specific procedures for randomization through the IRT are contained in the study procedures manual.

Subjects will be randomized in a 2:1 ratio to receive ASP2215 or salvage chemotherapy. Randomization will be stratified by response to first-line AML therapy and preselected salvage chemotherapy:

Response to first-line therapy:

- Relapse within 6 months after allogeneic HSCT
- Relapse after 6 months after allogeneic HSCT
- Primary refractory without HSCT
- Relapse within 6 months after CRc and no HSCT
- Relapse after 6 months after CRc and no HSCT

Preselected chemotherapy:

- High intensity chemotherapy (FLAG-IDA, MEC)
- Low intensity chemotherapy (LoDAC or azacitidine)

4 SAMPLE SIZE

This is a group sequential design based on co-primary endpoint of OS using the O'Brien-Fleming boundaries (non-binding) as implemented by Lan-DeMets alpha/beta spending method (East®).

The overall 0.025 one-sided type I error rate is allocated by 0.0005 and 0.0245 (corresponding to 0.001 and 0.049 for two-sided type I error rates) for the two co-primary efficacy endpoints of CR/CRh and OS, respectively. The type I error (alpha) in the first interim analysis is a nominal alpha which is arbitrarily selected for acknowledgement of the CR/CRh rate evaluation at the first interim and will not be recycled in the second interim analysis and final analysis.

Two interim analyses and one final analysis are planned. The first interim analysis is planned when approximately 141 subjects are randomized into ASP2215 arm and at least 112 days (4 treatment cycles) post first dose or randomization (for subjects who received no study drug). The second interim analysis is planned when approximately 129 death events have occurred and the final analysis is planned when approximately 258 death events have occurred.

OS:

Approximately 369 subjects (the planned sample size with 10% dropout rate) will be randomized in a 2:1 ratio to receive ASP2215 or salvage chemotherapy (246 subjects in the ASP2215 treatment arm and 123 subjects in the salvage chemotherapy arm). The planned 258 death events will provide about 90% power to detect a difference in OS between the ASP2215 arm with 7.7 months median survival time and salvage chemotherapy arm with 5 months median survival time (hazard ratio = 0.65) at the overall one-sided 0.0245 significance level.

CR/CRh rate:

The co-primary endpoint of CR/CRh rate will be evaluated only at the first interim analysis. One hundred and forty one subjects randomized to ASP2215 arm (211 subjects in total: 141 in the ASP2215 arm and 70 in the salvage chemotherapy arm) with a minimum follow-up of 4 treatment cycles are considered to achieve a maximum width of 15.78% for the two-sided 95% exact confidence interval (CI) when the CR/CRh is expected to be in the 5% to 30% range as summarized in the following table. A sample size of 141 subjects provides 80% power to exclude a CR/CRh rate of 12% using the two-sided 95% exact CI when the CR/CRh rate of ASP2215 is assumed to be 21%.

Table 1: Observed CR/CRh with Exact 95% CI (N=141 in ASP2215 arm)						
Observed CR/CRh (n and %)	95% Exact CI					
43 (30.50%)	(23.03%, 38.80%)					
36 (25.53%)	(18.57%, 33.55%)					
29 (20.57%)	(14.23%, 28.18%)					
28 (19.86%)	(13.62%, 27.41%)					
27 (19.15%)	(13.01%, 26.62%)					
26 (18.44%)	(12.41%, 25.84%)					
25 (17.73%)	(11.82%, 25.05%)					
24 (17.02%)	(11.22%, 24.26%)					
23 (16.31%)	(10.63%, 23.46%)					
22 (15.60%)	(10.04%, 22.66%)					
15 (10.64%)	(6.08%, 16.94%)					
8 (5.67%)	(2.48%, 10.87%)					

EFS and CR rate:

The planned sample size with 258 EFS events will provide about 90% power to detect the difference in EFS (6 months median EFS for ASP2215 arm and 3.9 months for salvage chemotherapy arm with hazard ratio = 0.65) and > 90% power to detect a difference in CR rate between ASP2215 (with 25% CR rate) and the salvage chemotherapy (with 10% CR rate) at the overall 1-sided 0.0245 significance level.

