6.1.3 Secondary Efficacy Endpoints

6.1.3.1 Key Secondary Efficacy Endpoints

• Event-free survival (EFS)

EFS is defined as the time from the date of randomization until the date of documented relapse (excluding relapse after PR), treatment failure or death from any cause within 30 days after the last dose of study drug, whichever occurs first [earliest of (relapse date, treatment failure date, death date) – randomization date + 1].

If a subject experiences relapse or death within 30 days after the last dose of study drug, the subject is defined as having EFS event related to either "relapse" or "death", and the event date is the date of relapse or death.

If a subject discontinues the treatment and fails to achieve any of the response of CR, CRp or CRi during the treatment period (subject with best response of PR or NR), the subject is defined as having EFS event related to treatment failure, and the event date is the randomization date. Subjects that discontinue the treatment with post-treatment disease assessment and best response of NE will be censored.

For a subject who is not known to have relapsed or treatment failure or death, EFS is censored at the date of last relapse-free disease assessment (last relapse-free disease assessment date – randomization date +1). Subject is not censored at HSCT. For subjects who are censored, last relapse-free disease assessment date refers to the subject's last disease assessment date. Subject without post-treatment disease assessment or without study treatment will be censored at randomization date.

EFS will be tested at the second interim and final analysis only when OS is rejected. No formal evaluation on EFS will be conducted at the first interim. During second interim analysis and final analysis, only death, relapse, treatment failure occurring on or prior to the cutoff date are counted as EFS events. Subjects without these events before cutoff date will be censored at the last relapse-free disease assessment date post-baseline on or before the cutoff date

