7.4 Analysis of Efficacy

There will be no efficacy analysis performed for the end of study report.

The significance levels at each interim and final analyses for each co-primary and secondary endpoints are specified in Table 4 below:

Table 4 Summary of Timing, Sample Size and Decision Guidance at the Planned Analyses

Analysis	Criteria for	Endpoint/	Efficacy B	Soundary*	Futility B	oundary*
	conduct of analysis (Projected timing)	Analysis Set	p-value (1-sided) at the Boundary	Approx. Observed HR at Boundary	p-value (1-sided) at the Boundary	Approx. Observed HR at Boundary
First Interim Analysis: CR/CRh rate	When 141 subjects are randomized into ASP2215 arm and at least 112 days (4 treatment cycles) post first dose or randomization (for subjects who received no study drug)	CR/CRh rate /2215 subjects in RAS	NA (0.0005 nominal)	NA	NA	NA
Second Interim	Approx. 129 OS	OS/ITT	0.00147	0.57	0.38674	0.95
Analysis:	events were observed	EFS/ITT	0.01519	0.67	0.30218	0.91
OS; EFS when null hypothesis of OS is rejected; CR rate when null hypotheses of both EFS and OS are rejected	Observed	CR rate/ITT	0.01519	NA	0.30218	NA
Final Analysis:	Approx. 258 OS	OS/ITT	0.02402	0.77	NA	NA
OS; EFS when	events were observed	EFS/ITT	0.01357	0.75	NA	NA
null hypothesis of OS is rejected; CR rate when null hypotheses of both EFS and OS are rejected	observed	CR rate/ITT	0.01357	NA	NA	NA

^{*:} P-value at both efficacy and futility boundaries (except the first interim) are based on 50% information fraction for OS, EFS and CR rate, and need update based on actual observed number of events at the second interim and final analysis.

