7.4.3 Analysis of Secondary Endpoints

7.4.3.1 Key Secondary Efficacy Analysis

The key secondary efficacy endpoint of EFS will be analyzed in the same manner as the co-primary endpoint of OS. In order to compare the EFS between ASP2215 and the salvage chemotherapy, the null hypothesis will be constructed:

• H₀₂: EFS in ASP2215 is worse or equal to EFS in salvage chemotherapy

The accompanying alternative hypothesis is:

• H₁₂: EFS in ASP2215 is better than EFS in salvage chemotherapy

To maintain the overall 1-sided Type I error rate at the 0.0245 significance level, the key secondary efficacy endpoint of EFS will be tested only at second interim and final analyses and only if the null hypothesis on OS (H_{01}) is rejected. The test significance levels of EFS endpoint at the second interim and final analyses are specified in Table 4.

The one-sided p-value for the above hypothesis test will be performed using the stratified log-rank test with strata (per IRT) to control for response to first-line AML therapy and preselected salvage chemotherapy.

The hazard ratio of the treatment effect along with 95% confidence interval will be calculated using stratified Cox proportional hazard model. The same stratification factors will be applied to both the stratified log-rank test and the stratified Cox proportional hazard model. The same Cox proportional hazard model will be included as a sensitivity analysis for testing H_{03} .

Kaplan-Meier survival plots will be used to describe the EFS in each treatment group. Median EFS and 95% confidence interval, EFS rates at 6, 12, 24 and 36 months and 95% confidence interval will be estimated from the Kaplan-Meier curve. The number and percentage of EFS event (relapse, death or treatment failure) and censoring will be summarized for each treatment group.

The sensitivity analyses for the key secondary efficacy endpoints of EFS include:

- The same analysis as primary analysis but on FAS
- The same analysis as primary analysis but on PPS
- Stratified Cox proportional hazard model with strata to control for response to firstline AML therapy and preselected salvage chemotherapy on ITT
- The same analysis as primary analysis but with the date of the first new anti-leukemia therapy after the end of study treatment or the last treatment evaluation date (when the date of new anti-leukemia is not available) will be used as the event date of treatment failure as defined in Section 6.1.3.1

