A nominal 1-sided p-value 0.0005 (i.e., 2-sided p-value 0.001) which is arbitrarily selected, will be spent to acknowledge the single-arm CR/CRh rate evaluation at the first interim analysis and will not be recycled in the second interim analysis and final analysis. No formal hypothesis testing will be conducted for CR/CRh rate for the study, only the descriptive statistics including two-sided 95% exact CI of CR/CRh rate will be provided to IDMC at the first interim. The hypothesis testing for the primary and secondary endpoints of OS, EFS and CR rate at the secondary interim analysis and final analysis are well controlled at an overall 1-sided type I error rate 0.0245 based on a sequential testing procedure.

Second Interim Analysis

The second interim analysis will be performed when approximately 50% of the total planned death events (death event = 129) have occurred for the study. OS will be tested at 1-sided 0.00147/0.38674 significant level for efficacy/futility according to the O'Brien-Fleming type alpha/beta spending function. The IDMC may recommend terminating the trial for favorable or unfavorable results at the second interim analysis based on OS endpoint, using the decision rules specified in table below:

Decision Rules based on 1-sided P-Value obtained at Second Interim Analysis

Overall Survival				
P-value ≥ 0.38674 0.38674>P-value ≥ 0.00147 P-value < 0.00147				
Unfavorable: Trial may be stopped for Futility	Trial continues	Favorable: Trial may be stopped for Efficacy		

The futility bound of this study is non-binding and is considered guidance rather than strict bound. Depending on the recommendations of the IDMC, the Sponsor may prepare a regulatory submission, if the outcome on OS at the second interim analysis is favorable.

If the study is not stopped after the second interim analysis, a final analysis based on OS will occur after 100% of the total planned death events (death events = 258) have been observed. The 1-sided significance level for the final analysis is 0.02402 for OS.

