According to the sequential testing procedure on controlling overall type I error rate for multiple endpoints, EFS will be tested when the null hypothesis of OS is rejected at the second interim or at the final analyses. CR rate will be tested when the null hypotheses of both OS and EFS are rejected hierarchically at the second interim or at the final analyses. Their significance levels at the second interim and final analyses will be based on Pocock/O'Brien-Fleming alpha/beta spending function. The details about the significance levels at each interim and final analyses for each co-primary and secondary endpoints are specified in Section 7.4 Table 4.

Details for the two formal interim analyses and the IDMC safety review procedures will be included in either Interim Analysis Plan (IAP) or IDMC Charter. The statistical analysis plan for the interim analyses will be described in interim analysis plan (IAP). Safety data including AE, lab, vital signs and ECG will be reviewed by IDMC on a periodic basis. The procedures for IDMC safety review will be described in the IDMC charter.

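### The stated EFS power of about 90% belongs to a single test at one-sided 0.0245; under the Pocock-type levels the SAP assigns to EFS, marginal power is about 87%

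*SAP*

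**What the plan says.** Section 4 (Sample Size) makes two parallel power statements. For OS: "The planned 258 death events will provide about 90% power to detect a difference in OS". For EFS: "The planned sample size with 258 EFS events will provide about 90% power to detect the difference in EFS", with the effect given as "6 months median EFS for ASP2215 arm and 3.9 months for salvage chemotherapy arm with hazard ratio = 0.65". Both refer to an overall one-sided level of 0.0245.

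The testing rules for EFS stand elsewhere in the SAP:

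- Section 6.1.3.1: "EFS will be tested at the second interim and final analysis only when OS is rejected".
- Section 7.4.3.1: "The test significance levels of EFS endpoint at the second interim and final analyses are specified in Table 4".
- Section 7.10, on EFS and CR rate: "Their significance levels at the second interim and final analyses will be based on Pocock/O'Brien-Fleming alpha/beta spending function".
- Section 7.4, Table 4: the one-sided efficacy levels for EFS are 0.01519 at the second interim and 0.01357 at the final analysis. For OS they are 0.00147 and 0.02402. The footnote says that the boundary p-values "are based on 50% information fraction for OS, EFS and CR rate, and need update based on actual observed number of events".

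The timing of both analyses depends on deaths. If the trial continues past the second interim, "a final analysis based on OS will occur after 100% of the total planned death events".

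**The concern.** The two endpoints share the same event count, hazard ratio, allocation and overall level, and are given the same power. Their boundaries differ. O'Brien-Fleming-type spending leaves OS almost the whole 0.0245 for the final analysis, so its power is close to that of a fixed test. Pocock-type spending uses much of the 0.0245 at the interim and leaves EFS only 0.01357 at the end, which costs power. The same events and effect cannot give about 90% under both sets of levels unless that cost is negligible.

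At stake is whether Section 4 describes the design in Table 4. The statement also does not say that it is a marginal figure, although EFS is reached only after OS is rejected.

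**Working it through.** **Inputs**

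- 258 EFS events and hazard ratio 0.65 (Section 4; 3.9/6 = 0.65).
- 2:1 allocation, 246 to 123 (Section 4), so the variance factor is (2/3)(1/3) = 2/9.
- Overall one-sided level 0.0245 (Section 4).
- EFS levels 0.01519 and 0.01357, information fraction 50% (Table 4 and its footnote).
- Futility bound non-binding (Section 7.10), so it is left out of the main figure.

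**Drift.** At the final analysis, −ln(0.65) × √(258 × 2/9) = 3.262. At half the information, 3.262/√2 = 2.306. The correlation between the two looks is √0.5.

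**Step 1: reproduce the stated figure.** For a single test at 0.0245 the critical value is z = 1.969. Power = Φ(3.262 − 1.969) = 90.2%, which matches Section 4.

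**Step 2: confirm the model against Table 4.**

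- Pocock-type spending at half information: 0.0245 × ln(1 + (e − 1) × 0.5) = 0.01519, the table's interim level. With 0.01357 at the final look, the total alpha is 0.0245.
- Boundary hazard ratio = exp(−z/√(D × 2/9)), where D is the number of events:

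| Endpoint | Look | D | Computed | Table 4 |
|---|---|---|---|---|
| EFS | interim | 129 | 0.667 | 0.67 |
| EFS | final | 258 | 0.747 | 0.75 |
| OS | interim | 129 | 0.574 | 0.57 |
| OS | final | 258 | 0.770 | 0.77 |

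Table 4 therefore rests on the same event count and variance as the power statement.

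**Step 3: power under the Table 4 levels.** Power = 1 − P(Z₁ < c₁ and Z₂ < c₂). Z₁ and Z₂ are bivariate normal with means 2.306 and 3.262 and correlation √0.5.

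| Endpoint | c₁, c₂ | Total alpha | Power, both looks | Final look alone |
|---|---|---|---|---|
| EFS | 2.165, 2.209 | 0.0245 | 86.9% | 85.4% |
| OS | 2.974, 1.977 | 0.0245 | 90.1% | 90.1% |

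A simulation of 4 million draws gives 86.9% for EFS. If the EFS futility level of 0.30218 were followed, power would be 85.9%.

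**Step 4: a cross-check from the futility levels.** At hazard ratio 0.65 and 129 events, the EFS futility level 0.30218 spends beta of 0.0369. Under O'Brien-Fleming-type beta spending at half information, that corresponds to a total beta of 0.140, or 86% power. The OS futility level 0.38674 spends 0.0218, a total beta of 0.105, or about 90% power. The table's own futility levels thus point to lower power for EFS than for OS.

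**Step 5: sensitivity of the marginal EFS power**

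- By number of EFS events at the Table 4 levels: 250 gives 85.8%, 270 gives 88.4%, 285 gives 90.0% and 300 gives 91.5%.
- With 258 events, 90% needs a hazard ratio of 0.636.
- If the Pocock-type levels are recalculated for an assumed EFS information fraction at the interim, power is 86.8% to 87.4% for fractions of 40% to 80%, and 88.4% at 90%.

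**Step 6: the OS gate.** The SAP gives no OS–EFS correlation, so 0, 0.5 and 0.9 are assumed, with the same drift for both endpoints and 2 million simulated trials each.

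| Rule | 0 | 0.5 | 0.9 |
|---|---|---|---|
| Gate applied at the interim only | 85.8% | 85.8% | 85.6% |
| Both rejected; EFS tested again at the final analysis after an interim OS success | 77.4% | 80.1% | 83.9% |
| Both rejected; trial stops after an interim OS success | 69.5% | 76.2% | 83.7% |

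**The case against.** The strongest defence is that the statement is hedged and names its basis, the overall 0.0245, on which 90.2% does reproduce. The shortfall is about 3 points, and a hazard ratio of 0.636 instead of 0.65 would close it. The 258 is also nominal: deaths trigger the analyses, and Table 4 says the levels will be updated to the observed events. EFS adds relapse and treatment failure to deaths, but counts deaths only within 30 days of the last dose and censors some subjects, so the count may fall on either side of 258. Finally, 86.9% is itself a convention. It ignores the OS gate and, like the 90%, assumes proportional hazards, although treatment failures are dated to the day of randomization.

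Much of this stands as a limit on the size of the point. The realised EFS power cannot be known from the plan, and the joint figures depend on assumptions that the SAP does not supply. It does not rescue the statement. The reference to an overall 0.0245 is also used for OS, where about 90% holds under the group sequential levels. For EFS, no section provides a single test at 0.0245. The power sentence itself fixes 258 events, and both the OS gate and the futility bound move power further below 90%.

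**Conclusion.** The concern holds, as a minor error. About 90% is the power of a fixed test at 0.0245. Under the boundaries the SAP prescribes for EFS, marginal power is 86.9%, about 3 points lower, so the type II error is about 13% and not about 10%. This rests on 258 EFS events, hazard ratio 0.65 with proportional hazards, 2:1 allocation, 50% information at the second interim, no OS gate and futility ignored.

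The probability of rejecting both OS and EFS is lower still: about 77% to 84% if EFS is retested at the final analysis after an interim OS success, and about 70% to 84% if the trial stops there, for assumed correlations of 0 to 0.9. The OS power statement is correct. Type I error, tests and estimates are unaffected.

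**What to change.** Replace the EFS power statement in Section 4 with about 87% for 258 EFS events and hazard ratio 0.65 under the Table 4 boundaries. Label it marginal, that is, before the OS gate and with the non-binding futility bound ignored. Add three points:

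- About 285 EFS events would give 90% on that basis.
- The actual EFS count may differ, because deaths trigger the analyses.
- The probability of rejecting both OS and EFS is lower. If a joint figure is given, state the assumed OS–EFS correlation.

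The cost is a short edit to one place in Section 4. No patients, levels, tests or estimates change. Version 4.0 plans no further efficacy analysis, so the correction only makes Section 4 agree with Table 4, with a slightly less favourable EFS figure.
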